10.3. Clinical assessments of Effectiveness

Effectiveness will be evaluated through assessments of body temperature, clinical symptoms of influenza, usual daily activities, appetite/eating patterns, incidence of influenza-related complications (see Section 11.4 for details), influenza virus titers, and changes in viral sensitivity to other antiviral drugs.

10.3.1. Body Temperature

Body temperature measurements will be recorded once at Screening/Baseline by the site's normal method, and then via an electronic thermometer provided by the Sponsor twice per day until temperature normalizes for 48 hours without the use of anti-pyretic medication. Acceptable means by which to record body temperature will be oral or axillary measurements. Study staff will record temperature measurements while the subject is on-site. Parents/care givers will be instructed to measure and record the subject's body temperature in the Subject Diary, using the electronic thermometer provided by the Sponsor. To avoid the confounding effects of antipyretic medications, temperature measurements will be taken, whenever possible, at least 4 hours after administration of any antipyretic medication or immediately prior to dosing. Temperature measurements that are recorded for the purpose of analyzing effectiveness in this study < 4 hours after administration of the antipyretic medication, regardless of the dose, will not be counted in the effectiveness analyses. The method of temperature measurement must be recorded.

10.3.2. Influenza Signs and Symptoms

Subjects (or parent/guardian) will be asked to provide an assessment of influenza symptoms on a 4-point severity scale (0, absent; 1, mild; 2, moderate; 3, severe) beginning pre-dose on Day 1 until symptom resolution and through the last follow-up visit, (whichever comes first). These assessments will be recorded on each day that the medical condition allows. Study staff will obtain this assessment pre-dose and post-dose on Day 1, and the subject's trained parent-guardian will then obtain it until returning to the site for the final visit. Influenza signs and symptoms vary by age. In addition, younger children may not be able to verbalize specific symptoms. Therefore, the assessment of influenza symptoms will be based on the subject's age, as follows:

- Parent/guardian of subjects birth to ≤ 3 years of age will provide/record an assessment of 5 influenza symptoms [cough, rhinitis, feverishness, malaise/irritability and gastrointestinal symptoms (nausea, vomiting or diarrhea)]
- Subjects ≥ 4 years of age to ≤ 6 years of age will be asked to provide an assessment of 7 influenza symptoms [cough, sore throat, nasal obstruction, myalgia (muscle aches), headache, feverishness, and gastrointestinal symptoms (nausea, vomiting or diarrhea)].
- Subjects 7 years of age and older will be asked to provide an assessment of 7 influenza symptoms (cough, sore throat, nasal obstruction, myalgia (muscle aches), headache, feverishness, and fatigue).

During the first visit, the study staff will instruct the parent/care giver on completing these assessments and recording responses directly into the Subject Diary. Although the parent/care giver will be recording the responses, the subject should be involved in the assessment of the symptoms.

10.3.3. Assessment of ability to perform usual daily activities

If possible, subjects or parents/care givers will be asked to provide a daily assessment of the subject's ability to perform usual daily activities using a 0-10 visual analogue scale, where 0 = Unable to perform usual activities at all, and 10 = Able to perform usual activities fully. The parent/care giver will be asked to record these assessments in the Subject Diary, with appropriate input from the subjects, once daily from Day 2 until resolution or the final follow-up assessment, whichever comes first.

10.3.4. Assessment of appetite and eating patterns

Subjects or parents/caregivers will be asked to provide a daily assessment of the subject's appetite and eating pattern as either normal or abnormal/reduced. The parent/ caregiver will be asked to record this assessment in the Subject Diary, with appropriate input from subjects, once daily from Day 2 until resolution or the final follow-up assessment, whichever comes first.

10.4. Virology Samples

Bilateral mid-nasal swab specimens will be collected for virologic analysis. Samples will be collected at Baseline, Day 3, Day 7, and, where possible, Day 14.

Virology laboratory tests will include viral sub type characterization from the baseline sample, laboratory culture and analysis by log₁₀ TCID₅₀, RT-PCR assay, viral susceptibility to peramivir, oseltamivir, and zanamivir, and genotypic analysis of primary virus isolates.

11. ASSESSMENT OF SAFETY

Safety will be evaluated through assessments of AEs, laboratory analyses (clinical chemistry, hematology, and urinalysis), vital signs, and physical examinations.

11.1. Adverse Events

Adverse events will be assessed and recorded at the indicated time points (see schedule of assessments, Table 1). AEs will be recorded on Day 1, Day 3, Day 7 and Day 14/Early Withdraw visits. Adverse events will be graded through use of the Division of Acquired Immune Deficiency Syndrome (DAIDS) Tables for Grading Adult and Pediatric Adverse Experiences (see Appendix 1). Any Grade 3 and Grade 4 clinical AEs or laboratory abnormalities that are judged to be possibly, probably, or definitely related to study treatment will be promptly (within 72 hours) reported to the study medical monitor unless the event meets criteria for an SAE, in which case they must be reported within 24 hours. Influenza-related complications are not considered AEs unless they meet the criteria for SAEs. Full details on recording and reporting AEs are provided in Section 11.1.2.

11.1.1. Definitions

11.1.1.1. Adverse Event

An AE is any untoward medical occurrence in a clinical study subject. No causal relationship with the study drug or with the clinical study itself is implied. An AE may be an unfavorable and unintended sign, symptom, syndrome, or illness that develops or worsens during the clinical study. Clinically relevant abnormal results of diagnostic procedures including abnormal laboratory findings (e.g., requiring unscheduled diagnostic procedures or treatment measures, or resulting in withdrawal from the study) are considered to be AEs.

Surgical procedures are not AEs but may constitute therapeutic measures for conditions that require surgery. The condition for which the surgery is required is an AE, if it occurs or is detected during the study period. Planned surgical measures permitted by the clinical study protocol and the conditions(s) leading to these measures are not AEs, if the condition(s) was (were) known before the start of study treatment. In the latter case the condition should be reported as medical history.

Assessment of the age appropriate symptoms of influenza symptoms will be documented and analyzed as a measure of effectiveness of the study treatment. These symptoms will not be reported as AEs unless the symptom(s) worsen to the extent that the outcome fulfills the definition of an SAE, which then must be recorded as such. Likewise, a RAT for influenza is required at screening in order to determine eligibility for the study, and therefore a positive RAT is not considered an AE.

AEs are designated as "nonserious" or "serious."

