#### 4.3. HANDLING OF DATA

#### 4.3.1. Strata and Covariates

Analyses will be presented by the stratification factor of age group at randomization.

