#### 6.3. SAFETY

#### **6.3.1.** Adverse Events

Adverse events will be mapped to a Medical Dictionary for Regulatory Activities (MedDRA) version 18.0 preferred term and system organ classification. If a subject experiences multiple events that map to a single preferred term, the greatest severity grade and strongest investigator assessment of relation to study medication will be assigned to the preferred term for the appropriate summaries. Should an event have a missing severity or relationship, it will be classified as having the highest severity and/or strongest relationship to study medication. Summaries of treatment-emergent AEs will include any AEs reported beginning with the initiation of study drug on Day 1. The occurrence of treatment-emergent adverse events (TEAEs) will be summarized by treatment group using preferred terms, system organ classifications, and severity. Separate summaries of treatment-emergent serious adverse events, treatment-emergent adverse events related to study drug, and events leading to the discontinuation of study will be generated. All adverse events reported will be listed for individual subjects showing both verbatim and preferred terms. All adverse events that occurred prior to the initiation of study treatment or more than 14 days post-study drug discontinuation will be excluded from the tables but will be included in the listings.

Missing onset dates will be imputed as previously outlined in Section 4.3.5 as required to determine treatment-emergent events.

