#### **6.3.3.** Clinical Laboratory Assessments

Descriptive summaries of the following selected (quantitative) clinical laboratory results will be presented by study visit and treatment group for each age group and overall: ALT, AST, Serum Creatinine, BUN, HGB, Albumin, and Alkaline Phosphatase. Laboratory abnormalities (toxicities) will be graded according to the DAIDS Table for Grading Adverse Events for Adults and Pediatrics (Publish Date: December 2004). The number and percentage of subjects experiencing treatment-emergent graded toxicities will be summarized by treatment group for each age group and overall. Laboratory toxicity shifts from baseline to Day 7 will be summarized by treatment group for each age group and overall.

All laboratory toxicities that occurred before the initiation of study treatment or more than 14 days post study drug discontinuation will be excluded from the tables but will be included in the listings.

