# **6.3.4.** Other Safety Analyses

Descriptive summaries of vital signs will be presented by study visit and treatment group for each age group and overall.

All abnormal physical examination findings will be summarized by study visit and treatment group for each age group and overall.

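### Non-serious nausea, vomiting and diarrhea count as adverse events only from age 7, so TEAE tables undercount them below 7 and any age-pooled GI rate mixes two definitions; SAP 6.3.1 omits the age split

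*Protocol*

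**What the plan says.** **AE rule.** Protocol 11.1.1.1 treats the age-appropriate influenza symptoms as effectiveness data: "These symptoms will not be reported as AEs unless the symptom(s) worsen to the extent that the outcome fulfills the definition of an SAE". The AE definition in SAP 4.3.8 repeats this. Protocol 10.3.2 sets the lists. From birth to 3 years the list ends with "malaise/irritability and gastrointestinal symptoms (nausea, vomiting or diarrhea"). From 4 to 6 years it ends with "headache, feverishness, and gastrointestinal symptoms (nausea, vomiting or diarrhea"). For older children, "Subjects 7 years of age and older will be asked to provide an assessment of 7 influenza symptoms (cough, sore throat, nasal obstruction, myalgia" opens a list with no GI item. The versions in the synopsis, Protocol 10.1 and SAP 2.1 differ in other items but agree on this one.

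**Tables.** Protocol 13.9 plans TEAEs by age group and treatment group. SAP 4.3.1 says "Analyses will be presented by the stratification factor of age group at randomization", and SAP 6 calls for age-group summaries where appropriate. SAP 6.3.1 says "The occurrence of treatment-emergent adverse events (TEAEs) will be summarized by treatment group using preferred terms, system organ classifications, and severity". The sections beside it are explicit about age: "treatment-emergent graded toxicities will be summarized by treatment group for each age group and overall" in 6.3.3, and "Descriptive summaries of vital signs will be presented by study visit and treatment group for each age group and overall" in 6.3.4. SAP 7 declares one change, an added analysis of antipyretic doses.

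**Populations.** Protocol 13.5 puts every subject given at least one dose in the Safety population. SAP 5.3 also requires that they were randomized.

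**Complications.** Under Protocol 11.1 and 11.4, influenza-related complications are not AEs unless serious. Protocol 13.9 lists their summary among the safety analyses. Protocol 10.3 and SAP 6.2.1 class them as effectiveness, and SAP Table 14.2.4 uses the ITTI population, which requires a positive RT-PCR.

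**The concern.** Safety is the primary objective, and diarrhea and vomiting were among the most frequent TEAEs in the earlier Japanese pediatric study (Protocol 5.3.2.1). A new, non-serious episode of vomiting after dosing is an AE in a seven-year-old. In a six-year-old it is a diary entry. The TEAE tables therefore understate GI events in the younger half of the planned sample, and a pooled rate describes neither half.

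The arms can be affected too. After amendment 3 all newly enrolled children under 7 receive peramivir, so the share of children whose non-serious GI events can count may differ by arm in a pooled table. Someone programming from SAP 6.3.1 alone would produce that pooled table.

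No planned output fills the gap. SAP 6.2.2 gives time to alleviation, including for individual symptoms by age group, but in ITTI. That is not the incidence of GI symptoms after dosing among treated children.

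Complications raise a related gap. Protocol 8.1 allows enrolment on symptoms alone during approved periods, so treated PCR-negative children can exist. A non-serious otitis media or pneumonia in such a child enters neither the AE tables nor Table 14.2.4.

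**Working it through.** **1. The plan's own numbers.** The age caps in Protocol 7.2 sum to 10 + 20 + 10 + 30 + 40 + 30 = 140. Under 7: 10 + 20 + 10 + 30 = 70. Aged 7 or over: 40 + 30 = 70, which at 4:1 is 56 peramivir and 14 oseltamivir. Protocol 13.4 gives about 117 on peramivir. Randomizing everyone from 28 days at 4:1 gives 10 + 0.8 × 130 = 114. Randomizing only from 2 years gives 30 + 0.8 × 110 = 118. The stated figure lies between these.

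**2. Oseltamivir children under 7.** Call this number k; the documents do not state it. Then peramivir N = 126 − k and oseltamivir N = 14 + k. Setting 126 − k = 117 gives k = 9. The SAP's design gives k = 40/5 = 8 if only ages 2 to under 7 were randomized, and k = 60/5 = 12 if those from 28 days were too.

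**3. Pooled GI rate, all treated children tabulated.** Assume one true rate p in both arms and at all ages, and that no non-serious GI event under 7 is recorded as an AE. The displayed rates are p × 56/(126 − k) and p × 14/(14 + k). With p = 16.2%, the diarrhea rate in the earlier pediatric study (uncontrolled, different dose):

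| k | Peramivir | Oseltamivir | Gap | One oseltamivir child |
|---|---|---|---|---|
| 8 | 56/118 × 16.2 = 7.7% | 14/22 × 16.2 = 10.3% | 2.6 points | 1/22 = 4.5 points |
| 9 | 56/117 × 16.2 = 7.8% | 14/23 × 16.2 = 9.9% | 2.1 points | 1/23 = 4.3 points |
| 12 | 56/114 × 16.2 = 8.0% | 14/26 × 16.2 = 8.7% | 0.8 points | 1/26 = 3.8 points |

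Fewer than 8 such children would widen the gap.

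**4. Unequal true rates.** Let r be the oseltamivir/peramivir ratio of true rates. The distortion of (peramivir − oseltamivir) is p × [−(70 − k)/(126 − k) + r × k/(14 + k)]. It changes sign at r = 1.44 for k = 8, 1.33 for k = 9 and 1.10 for k = 12. Above those values the pooled table works against peramivir. The documents give no value for r.

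**5. SAP 5.3 read literally.** If only randomized children are tabulated, k oseltamivir children under 7 go with 4k on peramivir. The countable shares are 56/(56 + 4k) and 14/(14 + k), which are equal. At k = 9 both are 60.9% (56/92 and 14/23). With equal true rates the arm gap is zero, but the undercount and mixed definition remain.

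**6. Size of the undercount.** If the earlier study's rates held in all 70 children under 7 and nothing were recorded, 70 × 0.162 = 11.3 children with diarrhea and 70 × 0.094 = 6.6 with vomiting would be missing. These are ceilings under that assumption, not estimates.

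**7. Complications.** The number missed depends on the PCR-negative share of treated children, which the documents do not give. It cannot be computed.

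**The case against.** The strongest reply is that keeping symptoms of the treated disease out of AE reporting is deliberate, and so are age-specific lists. That stands, and the AE definition should not change.

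It is also fair that the loss is partial. Protocol 11.1.2 tells investigators to record a diagnosis where one can be made, so gastroenteritis may still be entered below 7. The important-medical-event clause in 11.1.1.2 can capture significant GI events without hospitalization. A reader might infer that every non-serious GI event under 7 is lost; the documents do not support that.

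On the age split, Protocol 13.9, SAP 4.3.1 and SAP 6 all point to age-group tables, and SAP 6.3.1 does not exclude them. A reader might infer that the split was dropped. The text shows only that 6.3.1 is silent where its neighbours are explicit. A split at 7 would put one definition in each group, but would not recover the events missing below 7.

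For complications, ITTI is defensible for an effectiveness endpoint, and a child negative on every RT-PCR arguably has no influenza-related complication. But Protocol 13.9 also places this summary under safety, where 13.5 calls for all treated subjects. Nor do the data vanish: serious complications reach the TEAE and SAE tables, antibiotics reach Table 14.3.8, and the events are in Listing 16.2.6.8.

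**Conclusion.** The definition changes at age 7. TEAE tables will understate non-serious GI events in children under 7 by an unknown amount, and any age-pooled GI AE rate mixes two definitions. This follows from the text and needs no assumption about rates.

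The effect on the arm comparison is small and conditional. With all treated children tabulated, equal true rates and 8 to 12 oseltamivir children under 7, it is 2.6 to 0.8 points toward peramivir, less than one oseltamivir child. A reader might infer a much larger distortion by assuming that no child under 7 received oseltamivir: 56/126 × 16.2% = 7.2% against 16.2%, or 9.0 points. That implies 126 on peramivir, which does not fit the stated figure of about 117. It also sits badly with the synopsis, which says the 2 to 7 year cohort was partly enrolled under randomization to either drug. Nor is a fixed direction supported, since unequal true rates can reverse it.

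The complications gap is real for planned summaries, of unknown size, and carries no claim about direction. No hypothesis is tested, so the consequence is a misleading description of the primary safety data. Severity is minor to should-fix.

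**What to change.** All changes are to the SAP; the AE definition stays.

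1. In SAP 6.3.1 and Tables 14.3.1.1 to 14.3.1.4, state that TEAEs are presented by age group and treatment group, using the five age groups of Protocol 13. Use the Safety population of Protocol 13.5 (all treated) and correct SAP 5.3 to match. Footnote that non-serious GI symptoms are not AEs under age 7. Limit the between-arm comparison of GI AEs to age 7 and over.
2. Optionally, add a descriptive table of new or worsened diary GI symptoms in all treated children under 7, by age group and arm. Use observed values only and do not pool them with AEs. Note that the item combines nausea, vomiting and diarrhea, and that recording stops at symptom resolution.
3. Also run Table 14.2.4 on all treated subjects, counting complications diagnosed after the first dose, and keep the ITTI version.

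The cost is some wording, a footnote and up to two small tables from data already collected. The diary table will include illness symptoms and will not make younger and older children comparable. The remaining GI comparison rests on about 14 oseltamivir children, where one child is 1/14 = 7.1 points.

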11.1.1.2. Serious Adverse Event

An SAE is an adverse event that results in any of the following outcomes:

- Death
- Is life-threatening (subject is at immediate risk of death at the time of the event; it does not refer to an event that hypothetically might have caused death if it were more severe)
- Requires in-subject hospitalization (formal admission to a hospital for medical reasons) or prolongation of existing hospitalization
- Results in persistent or significant disability/incapacity (i.e., there is a substantial disruption of a person's ability to carry out normal life functions)
- Is a congenital anomaly/birth defect

Important medical events that may not result in death, are not life-threatening, or do not require hospitalization may be considered an SAE when, based upon appropriate medical judgment, they may jeopardize the subject or may require medical or surgical intervention to prevent one of the outcomes listed in this definition. Examples of such events include allergic bronchospasm requiring intensive treatment in an emergency room or at home, blood dyscrasias or convulsions that do not result in subject hospitalization, or the development of drug dependency or drug abuse.

Hospitalization, as per the institution's standard of care (SOC) to treat pediatric influenza is not considered an SAE and should not be reported as such. Any adverse event the causes a prolongation of an existing hospitalization must be reported as per Section 11.1.5.

11.1.2. Method, Frequency, and Time Period for Detecting Adverse Events and Reporting Serious Adverse Events

Reports of AEs are to be collected from the time the subject consents to participate through the follow-up period ending on Day 14. The Investigator or designee must completely and promptly record each AE. The Investigator should attempt, if possible, to establish a diagnosis based on the presenting signs and symptoms. In such cases, the diagnosis should be documented as the AE and not the individual sign/symptom. If a clear diagnosis cannot be established, each sign and symptom must be recorded individually. If a final diagnosis is established during evaluation or treatment, the source documents will be updated accordingly.

The Investigator should attempt to follow all unresolved AEs and/or SAEs observed during the study until they are resolved, or are judged medically stable, or are otherwise medically explained.

11.1.3. **Definition of Severity**

All AEs will be assessed (graded) for severity and classified using the DAIDS criteria for grading AEs (see Appendix 1). Any adverse events not covered by the DAIDS criteria will be assessed and classified into one of three clearly defined categories as follows:

Protocol Version 6.0

BioCryst Pharmaceuticals, Inc. CONFIDENTIAL

BCX1812-305

Mild: (Grade 1): Transient or mild symptoms; no limitation in activity; no

intervention required. The AE does not interfere with the participant's

normal functioning level. It may be an annoyance.

Moderate: (Grade 2): Symptom results in mild to moderate limitation in activity;

no or minimal intervention required. The AE produces some impairment of functioning, but it is not hazardous to health. It is uncomfortable or an

embarrassment.

Severe: (Grade 3): Symptom results in significant limitation in activity; medical

intervention may be required. The AE produces significant impairment

of functioning or incapacitation.

Life threatening (Grade 4): Symptoms causing inability to perform basic self-care

functions OR Medical or operative intervention indicated to prevent

permanent impairment, persistent disability, or death

